10.7.3 Definition of Mild, Moderate and Severe COVID-19 Cases

Mild COVID-19 cases are defined as virologically (RT-PCR) confirmed cases fulfilling **all** of the following:

- Symptomatic,
- No shortness of breath or difficulty breathing,
- No hypoxemia, i.e. Oxygen saturations in arterial blood (SpO₂) saturation $\geq 95\%$ on room air at sea level; SpO₂ should be adjusted according to altitude.
- Does not meet the case definition of moderate or severe COVID-19

Moderate COVID-19 cases are defined as virologically (RT-PCR) confirmed cases fulfilling **any** of the following criteria:

- Shortness of breath or difficulty breathing
- Respiratory rate ≥ 20 to < 30 breaths per minute
- Abnormal SpO₂, but still $> 93\%$ on room air at sea level; SpO₂ should be adjusted according to altitude.
- Clinical or radiographic evidence of lower respiratory tract disease
- Radiologic evidence of Deep Vein Thrombosis

Severe COVID-19 cases are defined as virologically (RT-PCR) confirmed cases fulfilling **any** of the following:

- Clinical signs at rest indicative of severe systemic illness (respiratory rate ≥ 30 per minute, heart rate ≥ 125 per minute, SpO₂ $\leq 93\%$ on room air at sea level or Arterial Oxygen Partial Pressure /Fractional Inspired Oxygen (PaO₂/FIO₂) < 300 mmHg); SpO₂ should be adjusted according to altitude.
- Respiratory failure (defined as needing high flow-oxygen, noninvasive ventilation, mechanical ventilation or Extracorporeal membrane oxygenation (ECMO))
- Evidence of shock (systolic blood pressure (SBP) < 90 mmHg, diastolic blood pressure (DBP) < 60 mmHg, or requiring vasopressors)
- Significant renal, hepatic, or neurologic dysfunction
- Admission to Intensive Care Unit (ICU)
- Death

A fourth category of “moderate to severe” cases is further defined, combining cases of moderate severity and cases of severe severity.

10.7.4 COVID-19 Case Definition for Efficacy Analysis

A case of COVID-19 meeting the case definition for efficacy analysis is defined as follows:

- Virologically-confirmed case of COVID-19 (of any severity) defined as a positive SARS-CoV-2 specific RT-PCR test in a person with clinically symptomatic COVID 19, see Section 10.7.2.
- Symptom onset ≥ 15 days after second trial vaccination, i.e.

$$\text{Start date of symptoms} - \text{date of second vaccination} \geq 15 \text{ days.}$$

See Section 10.7.2 for further details on definition of symptom onset.

- First episode of virologically-confirmed COVID-19, i.e. the subject must not have a history of virologically-confirmed COVID-19 illness at enrollment or have developed a case of virologically-confirmed COVID-19 before 15 days after the second trial vaccination.
- Subject is SARS-CoV-2 naïve at baseline and Day 43 (defined as seronegative to N protein in the blood samples collected at baseline and Day 43). See Section 10.6.1 for further details.

10.7.5 Adjudication of COVID-19 Cases

An independent Committee of clinicians is formed to adjudicate some COVID-19 cases, and asymptomatic cases of SARS-CoV-2 infections (Section 10.8). The Committee is blinded to the treatment assignment of the subject. The cases are adjudicated by the members with respect to the following questions:

- Is the case a virologically-confirmed case of COVID-19 defined as a positive SARS-CoV-2 specific RT-PCR test in a person with clinically symptomatic COVID-19 with one or more of the symptoms listed in Section 10.7.1?
- Was the RT-PCR test performed at the CureVac designated central laboratory?
- Was the symptom onset of the case ≥ 15 days following the second vaccination? Or did it occur before 15 days following the second trial vaccination?
- Was the subject naïve or non-naïve to SARS-CoV-2 at baseline and Day 43? (defined as being seronegative or seropositive to the SARS-CoV-2 N protein at baseline and Day 43).
- Was the subject 18 to 60 years of age or ≥ 61 years of age?
- Was the subject asymptomatic? If asymptomatic, was the RT-PCR test positive ≥ 15 days following the second vaccination or before?
- Was it a mild, moderate, or severe case of COVID-19 based on the provided clinical definitions?
- Did the subject require supplemental oxygenation? What type of oxygen support did the subject receive?
- Was the subject hospitalized? Was the subject admitted to the ICU?
- Did the subject die? Due to COVID-19 or other cause?

NB: The Adjudication questionnaire uses the term “CureVac designated central laboratory” although in this study the local laboratory had been designated by CureVac to perform the RT-PCR test.

COVID-19 case summary data as provided by the Adjudication Committee is used for all relevant definitions and analyses, i.e. especially all efficacy cases have to be confirmed by the Adjudication Committee. Where the adjudicated data conflicts with other data recorded on the CRF (e.g. severity of the event, or baseline serology status), the adjudication data generally overrules the other data available. This applies to both COVID-19 cases and asymptomatic cases of SARS-CoV-2 infections.

Exceptions:

1. For the analysis of COVID-19 cases by age group, the age at trial entry as recorded on the CRF rather than the age at onset (as assessed by the Adjudication Committee) is used.
2. The case onset date is also taken from the CRF, irrespective from the onset date recorded on the Adjudication Form.

10.8 Definition of Asymptomatic Cases of SARS-CoV-2 Infection and Onset Date

There is no active surveillance in this trial for asymptomatic SARS-CoV-2 infections. Subjects are reminded to contact the trial site immediately if he/she had a positive SARS-CoV-2 test performed outside of the trial site, whether or not they were symptomatic (COVID-19 illness) or asymptomatic at the time of the test.

If the subject was asymptomatic, trial staff contacts the subject immediately to collect information about the positive SARS-CoV-2 test the subject reported. The subject should be retested as soon as feasible to confirm the result. A positive RT-PCR test result is considered definitive as a virologically-confirmed case of SARS-CoV-2 infection.

If the subject is confirmed to have SARS-CoV-2 infection, the subject is followed by trial staff for at least 2 weeks for the development of any COVID-19 symptoms, to ensure that this is an asymptomatic infection. If the subject develops COVID-19, he/she is followed up as a COVID-19 case. If the subject is confirmed to be an asymptomatic infection, information is collected by the trial staff and documented on the appropriate CRF page.

The onset date of an asymptomatic infection is defined as the date of the positive RT-PCR test result performed by a central laboratory.

10.9 Burden of Disease

Two different BoD scores are calculated for each subject, based on their first episode of virologically confirmed COVID-19 case meeting the case definition for efficacy analysis.

BoD Score #1 is assigned as follows (considering only first episodes):

- No disease (i.e. not infected or only asymptomatic infection): Score = 0
- Mild or moderate disease (as defined in Section 10.7.3): Score = 1
- Severe disease (as defined in Section 10.7.3): Score = 2

BoD Score #2 is assigned as follows (considering only first episodes):

- No disease (i.e. not infected or only asymptomatic infection): Score = 0
- Disease without hospitalization: Score = 1
- Disease with hospitalization: Score = 2
- Death: Score = 3.

- If the case start day and the unblinding day occur on the same day the case counts for the analysis. (Censoring starts at the day after the unblinding.)

The following details are to be followed regarding censoring the day after receiving the AV:

- Times are not relevant as neither AV time nor case start time are collected.
- If AV date is complete then censoring starts at first day after the AV day.

- If AV date is incomplete (only day missing) then censoring starts after this month.
- If AV date is incomplete (month missing, year available) then censoring starts after this year.
- If AV date is completely missing then no censoring can be made.

As these imputations of incomplete AV dates are not an ideal solution this is only to be considered as a fallback solution in case complete AV dates cannot be retrieved and an interim workaround for unclear data during study conduct.

All incomplete or missing AV dates need to be queried.

10.11 Event Dates, Follow-Up Time, Time to Event Calculation and Censoring

Subject's follow-up time and rules for time to event calculations and censoring are dependent on the definition of the endpoint analyzed.

General formulae for the calculation of follow-up time and time to event are provided below. Table 8 further summarizes the definitions and derivations for the dates to be included in the respective formulae based on the endpoint analyzed.

- For each subject, the follow-up time (days) is defined as:

$$\text{Follow Up Time (days)} = \text{End date of Follow Up} - \text{Start date of Follow Up} + 1.$$

- For each event type, the total follow-up time within each vaccine group is calculated as the sum of all single follow-up times in that group. The total follow-up (years) is calculated as

$$\text{Total Follow Up Time (years)} = \frac{\text{Total Follow Up time (days)}}{365.25}$$

- The time to event (days) for both subjects with an event and censored subjects are calculated as follows:

$$\text{Time to Event (days)} = \text{Event/Censoring Date} - \text{Start Date} + 1.$$

Table 8: Event Dates, Censoring and Follow-Up Time Calculation

Endpoint Short Description	Start Date	Event Date*	Censoring Date [#]	End Date of Follow-Up
First episodes of COVID-19 cases ⁺	2 nd vac. + 15 days	Date of symptoms onset	Min (unblinding date + 1; date AV + 1; trial termination date; cut-off date [^])	Min (Event date; Censoring date)
First episodes of moderate to severe COVID-19 cases	2 nd vac. + 15 days	Date of symptoms onset	Min (first episode of mild COVID-19 case date; date AV + 1; unblinding date + 1; trial termination date; cut-off date [^])	Min (Event date; Censoring date)
First episodes of severe COVID-19 cases	2 nd vac. + 15 days	Date of symptoms onset	Min (first episode of mild or moderate COVID-19 case date; date AV + 1; unblinding date + 1;	Min (Event date; Censoring date)

Endpoint Short Description	Start Date	Event Date*	Censoring Date [#]	End Date of Follow-Up
First episodes of moderate COVID-19 cases	2 nd vac. + 15 days	Date of symptoms onset	trial termination date; cut-off date [^]) Min (first episode of mild or severe COVID-19 case date; date AV + 1; unblinding date + 1; trial termination date; cut-off date [^])	Min (Event date; Censoring date)
First episodes of mild COVID-19 cases	2 nd vac. + 15 days	Date of symptoms onset	Min (first episode of moderate or severe COVID-19 case date; date AV + 1; unblinding date + 1; trial termination date; cut-off date [^])	Min (Event date; Censoring date)
BoD Scores	2 nd vac. + 15 days	Date of symptom onset of corresponding COVID-19 case	Min (unblinding date + 1; date AV + 1; trial termination date; cut-off date [^])	Min (Event date; Censoring date)
Second episode of Covid-19	Resolution date of first primary case episode	Date of symptoms onset of a second COVID-19 case	Min (unblinding date + 1; date AV + 1; trial termination date; cut-off date [^])	Min (Event date; Censoring date)

Vac = Vaccination

+ For endpoints assessed in naïve subjects as well as endpoint assessed in subjects regardless of their baseline serology status

* Only events with an onset date \geq start date are considered

[#] Only for subjects without an event with an onset date \geq start date

[^] e.g. in case of an IA

^{\$} Date of symptom onset of a virologically-confirmed COVID-19 case. After such a case, subject can no longer be considered an "asymptomatic" subject.

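### SAP 10.11 counts one day too many for each event-free subject censored by unblinding or authorized vaccine: Table 8 and the follow-up formula each add a day

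*SAP*

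**What the plan says.** SAP 10.10 fixes which days can contribute a case. On unblinding it says "If the case start day and the unblinding day occur on the same day the case counts for the analysis", and adds "Censoring starts at the day after the unblinding". The AV rule is parallel: "If AV date is complete then censoring starts at first day after the AV day". Data from the censoring point onward go to listings only. Table 7 applies whichever of the two dates is earlier.

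SAP 10.11 defines the person-time:

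- Follow-up starts at "2 nd vac. + 15 days".
- It ends at "Min (Event date; Censoring date").
- For first episodes of any severity the censoring date is "Min (unblinding date + 1; date AV + 1; trial termination date; cut-off date"). It applies, per the footnote, "Only for subjects without an event with an onset date" on or after the start date.
- Follow-up in days is the end date minus the start date, with a closing "+ 1" in the formula ("Start date of Follow Up} + 1").

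The unblinding and AV terms carry their own added day in every row of Table 8. The trial termination date, the cut-off date and the event date do not.

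SAP 12.8.1.1 sums these times by arm and uses their ratio, r, in VE and in both confidence limits. SAP 12.8.1.2 does the same for mild cases.

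**The concern.** The two added days do different jobs. In Table 8, adding a day to the unblinding or AV date gives the first day that is no longer at risk. In the formula, adding a day treats the end date as at risk. Applied to the same subject, they put a day into the denominator that 10.10 has removed from the numerator.

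The mismatch is not a convention applied evenly to everyone. Subjects who end at an event, at trial termination or at a cut-off are counted correctly, so one denominator mixes two counting rules. Protocol 7.3.3.2 and SAP 8.6 provide for unblinding all subjects, so the miscounted group could be most of the efficacy set. Total follow-up time is itself a reported output, and r is the only route by which exposure enters VE.

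**Working it through.** **Inputs.** Start S = second vaccination + 15 days (Table 8). L = the earlier of unblinding date and AV date, the last day on which a case counts (10.10). Follow-up = end − start + 1 (10.11). Planned size 2,520, with 1,680 on pooled CVnCoV and 840 on placebo (SAP 8.1, 8.5.1). The plan states no person-time total, case count or VE for this trial, so there is no figure to reproduce.

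**Days per subject**

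- Days on which a case can count: S to L inclusive = L − S + 1.
- Days credited by Table 8 and the formula: (L + 1) − S + 1 = L − S + 2.
- Surplus: 1 day. Enumerating unblinding from 0 to 364 days after S, with no AV date or with AV dates at weekly steps over the same range, gave a surplus of exactly 1 in every combination.
- Ending at trial termination or cut-off 100 days after S: 101 days credited, 101 countable, surplus 0.

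**Example (invented dates).** Second vaccination 1 March 2021, S = 16 March, unblinded 14 May, no event. Countable days: 16 in March + 30 in April + 14 in May = 60. Table 8 ends follow-up on 15 May, so 61 are credited.

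**Limiting case.** A subject unblinded on S itself stays in the Efficacy Analysis Set, because SAP 9.5.5 excludes only those unblinded or given AV earlier than that day. This subject is credited with 2 days for 1 countable day.

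**Upper bound on total person-time.** If all 2,520 were censored this way: 1,680/365.25 = 4.60 and 840/365.25 = 2.30 years, together 6.90 person-years.

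**Effect on a rate.** If everyone in a group is censored this way and mean at-risk time is F days, the rate is multiplied by F/(F + 1), an understatement of 1/(F + 1). F = 60: 1/61 = 1.6%. F = 30: 1/31 = 3.2%. These values of F are assumptions.

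**Effect on VE.** VE = 1 − [p/(1 − p)]/r, so only the change in r matters. The rows below start from 48.2%, the HERALD result in the Protocol synopsis (relative risk 0.518), and use assumed follow-up. They show direction and order of size only.

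| Mean days, CVnCoV / placebo | Who is censored this way | r, correct → as written | VE as written |
|---|---|---|---|
| 60 / 60 | all | 2.000 → 2.000 | 48.20% |
| 60 / 30 | all | 4.000 → 2×61/31 = 3.935 | 47.35% |
| 30 / 30 | placebo only | 2.000 → 2×30/31 = 1.935 | 46.47% |
| 30 / 30 | CVnCoV only | 2.000 → 2×31/30 = 2.067 | 49.87% |

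**The case against.** The best defence of the text is that the Table 8 footnotes, read alone, set no upper limit on event dates. A case on the day after unblinding might then seem countable, and the extra day would be legitimate exposure. SAP 10.10 rules this out, because censoring has started by then and data from that point are only listed.

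The stronger defence concerns consequence, and most of it stands. VE moves only if the arms differ in follow-up or in the share censored, and the plan gives no reason to expect much difference. Under 10.10, subjects ask to be unblinded in order to decide about an AV, so the request is made before the arm is known. Choices made after disclosure, including the withdrawal of placebo subjects, follow the censoring date. Protocol 9.4.2 describes AV use at varying times in all groups. Efficacy is secondary and descriptive, without success criteria (Protocol 10.3.7.1), and VE is now computed only for any-severity and mild cases.

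Two stronger readings are tempting but unsupported:

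- **A directional VE bias.** A reader might infer that VE is understated because placebo subjects leave earlier. The documents give no follow-up by arm, and the shift can go either way.
- **A ceiling on follow-up.** A reader might take 11 February 2021 (SAP 6.1 footnote) to the Protocol version 3.0 date of 23 July 2021, 162 days, subtract 28 + 15, and call 119 days the maximum. It is not a bound. The first date is the last randomisation date of one delivery cohort, so others could start earlier, and the Protocol synopsis ties the end of blinding to approval of version 3, not to its document date.

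**Conclusion.** The miscount is established from SAP 10.10 and 10.11 alone and needs no assumption: exactly one surplus day for each event-free subject whose follow-up ends through unblinding or AV, and none for anyone else. No other section corrects it.

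Its consequence is small. The person-time surplus cannot exceed 6.9 person-years at the planned size. The percentage effect on rates depends on mean at-risk time, which the documents do not state. VE is exactly unchanged under equal follow-up and equal censoring, and any other VE figure is illustrative. It is a minor specification error that is cheap to remove, and it does not support a claim that VE in this trial is materially biased.

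**What to change.** For the any-severity and mild endpoints, and in the other Table 8 rows for consistency, set the end of follow-up to the minimum of event date, unblinding date, AV date, trial termination date and cut-off date. Keep the existing terms for first episodes of another severity, and keep the inclusive formula. Where an AV date is incomplete, the 10.10 rule implies that the last day at risk is the end of the known month or year.

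Editing Table 8 alone would leave it out of step with 10.10 and Table 7, which describe censoring at the first day after. State in both sections that the unblinding or AV date is the last day at risk and the following day is the first censored day. An equivalent route is to keep the later date as the censoring date and omit the inclusive added day for these subjects only. The time-to-event formula in 10.11 has the same form and should follow the same rule, although the effect there is close to nil.

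The cost is wording in two SAP sections and a small programming change, with no new data. Because SAP version 4.0 was written by an unblinded team (SAP 6.0), record the change as a rule-based correction, applied to both arms alike and made before database lock.

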10.12 Age Group

Subjects are assigned to the age groups "18 to 60 years" and " \geq 61 years" based on the age recorded in the IWRS. If age is missing in the IWRS then age group is assigned based on age derived from year of birth recorded in the IWRS and date of first informed consent (age = year of date of informed consent – year of birth).

11.0 Interim Analyses

No formal IA is done. In August 2021 a first immunogenicity delivery is provided.

12.0 Statistical Methods

Unless otherwise noted, categorical variables are summarized using counts and percentages. Percentages are presented with one decimal place, except 100% is displayed without any decimal places and percentages are not displayed for zero counts. Continuous variables are summarized using the number of observations (n), mean, median, SD, 1st Quartile (Q1), and 3rd Quartile (Q3), minimum and maximum values. Mean, median, Q1 and Q3 are presented to 1 decimal more than original data. SD is presented with 2 decimals more than original data. Minimum and maximum match the decimal points in the original data. The maximum number of decimals is 4, unless otherwise stated.

In general, all data summaries are presented overall and by vaccine group. Thereby, the CVnCoV data is presented for pooled CVnCoV lots and split by lot. Efficacy outputs are not split by lot and do not have an overall column presented. Selected outputs are **additionally** presented using further subsetting of the data. This is specified explicitly in the respective sections.

If not stated otherwise, p-values from statistical tests are two-sided and CIs are calculated using a 95% confidence level.

Age group is used as a factor for stratification of randomization. The efficacy analyses are in general **not** adjusted for this factor.

No imputation of missing data other than that described in Section 10.3 is performed.

All data collected during this trial is displayed in data listings, unless otherwise specified. Screening failures are excluded from all listings and tables if not otherwise stated. Listings include all relevant assigned/derived variables. If not explicitly stated, listings do not show imputed data, but present data as reported.

All data summaries and tabulations are prepared using SAS® Version 9.4 or higher.

In agreement with the sponsor it was decided to not perform some of the analyses in the EOT analysis. Therefore some of the below analyses were never performed. For details, please refer to Appendix 4

